------------	-------------------	-------

22 Aug 2017

ABBREVIATIONS

AAS	Angioedema Activity Score		
AE-QoL	Angioedema Quality of Life (questionnaire)		
AUC	Area Under the Curve		
EQ-5D-5L	EuroQol 5-Dimensional 5-Level Descriptive System		
EQ-VAS	EuroQol Visual Analogue Scale		
HAE	Hereditary Angioedema		
HRU	Healthcare Resource Utilization		
HRUA-HAE	Healthcare Resource Utilization Assessment related to HAE		
HRQoL	Health Related Quality of Life		
MCID	Minimal Clinical Important Difference		
MDC ₉₅	Minimal Detectable Change with 95% confidence		
NNA	Normalized Number of Attacks		
PRO	Patient Reported Outcome		
RD	Responder Definition		
SAP	Statistical Analysis Plan		
SC	Subcutaneous		
SD	Standard Deviation		
SDS	Sheehan Disability Scale		
SE	Standard Error		
SEM	Standard Error of Measurement		
VAS	Visual Analogue Scale		
WPAI-GH	Work Productivity and Activity Impairment - General Health (questionnaire)		

1. INTRODUCTION

This Statistical Analysis Plan (SAP) outlines the analyses to be conducted on the Patient Reported Outcome (PRO) data for Study SHP616-300: A Phase 3, randomized, double-blind, placebo-controlled, two-period, three-sequence, partial crossover study to evaluate the efficacy and safety of subcutaneous (SC) administration of 2000 IU of C1 esterase inhibitor [human] liquid for injection for the prevention of angioedema attacks in adolescents and adults with hereditary angioedema (HAE). Specifications for PRO tables and figures will be provided in a separate document.

The primary efficacy endpoint in SHP616-300 is the normalized number of angioedema attacks (NNA) during a treatment period, measured as observed. The impact of treatment on health related quality of life (HRQoL), health status, work, and activity impairment due to health, disability, and disease symptoms were assessed as secondary endpoints using several PROs: Angioedema Quality of Life Questionnaire (AE-QoL), EuroQol 5-dimensional 5-level (EQ-5D-5L) descriptive system, and the EuroQol Visual Analogue Scale (EQ-VAS), Work Productivity and Activity Impairment Questionnaire - General Health (WPAI-GH), Sheehan Disability Scale (SDS), and Angioedema Activity Score (AAS). Healthcare resource utilization (HRU) data are also collected as part of the study. This document outlines the analyses to be conducted on the PRO and HRU data.

2. STUDY DESIGN

2.1 Study Design Overview

Data will be collected in Study SHP616-300, a phase 3, randomized, double-blind, placebocontrolled, two-period, three-sequence, partial crossover study to evaluate the efficacy and safety of SC administration of 2000 IU of C1 esterase inhibitor [human] liquid for injection for the prevention of angioedema attacks in adolescents and adults with HAE. The trial uses a partial Balaam's cross-over study design with two periods (each lasting 14 weeks), two treatments (active and placebo), and three treatment sequence groups (Exhibit A). The Study Design Flow Chart is shown in Exhibit B.

This multicenter study is being conducted at approximately 40 sites globally (North America and EMEA). The study aims to screen 75 subjects, enroll 66, and ensure that 54 subjects complete both study periods. Treatment sequence groups 1 (AB) and 2 (BA) will each contain 26 subjects, with treatment sequence 3 (AA) containing 14 subjects.

Treatment Sequence	Treatment Period 1	Treatment Period 2	Approximate Number of Subjects Randomized
1 (AB)	А	В	26
2 (BA)	В	А	26
3 (AA)	А	А	14

Exhibit A: Treatment Sequences

Treatment A: 2000 IU (4.0 mL) C1 esterase inhibitor [human] liquid for injection administered SC twice weekly (every 3 or 4 days) for 14 weeks.

Treatment B: Placebo (4.0 mL) administered SC twice weekly (every 3 or 4 days) for 14 weeks.

2.2 The Cross-over Design

A cross-over design is one in which the effects of different treatments (here C1 esterase inhibitor [human] liquid for injection and placebo) are compared on the same subject during different study periods. This study design was chosen as the best way to jointly address the protocol objectives of establishing efficacy (relative to placebo) and safety (i.e., adequate numbers of subjects for precision of estimation in detecting potential safety signals). An advantage of such a design is that a comparison of treatments on the same subject is expected to be more precise than a comparison between subjects and therefore to require fewer subjects for the same precision.

The simple analysis of a cross-over trial assumes that the effect of treatment is the same during each study period, i.e., that the effect of any treatment given during the second period is not influenced by the treatment received in the first. This assumption, no interaction between treatment and period, can be tested. Hills and Armitage (1979) provide a comprehensive overview of the fundamentals of cross-over trial design and analysis.

22 Aug 2017

Exhibit B: Study Design Flow Chart

2.3 Study Design Considerations

The present trial uses a partial Balaam's cross-over study design with two periods (each lasting 14 weeks), two treatments (active and placebo), and three treatment sequence groups: AB, BA, AA (Exhibit A). Balaam (1968) proposed a design-based approach to assess the problem of carry-over effects, by pointing out that if the AB/BA design were extended to include the sequences AA and BB, then within-subject estimates of a direct treatment effect could be obtained even in the presence a carryover effect. However, Balaam's design was able to achieve this because it assumed a particular model for the carryover effect which no longer enjoys wide support (Senn, 2002). The Balaam's design is typically chosen to when it is hypothesised that there is a self-carryover effect, i.e., the response during the second period on the same treatment is affected by the response during the first study period, or when there is a treatment by period interaction. In this study, a partial Balaam's design is used, in the absence of a BB sequence group; the Balaam's design is not completely balanced. The Balaam's design is particularly relevant since there will be no washout between the 2 study periods, each of 14 weeks. The omission of a washout period is to minimize the duration that subjects will be without active treatment.

In this trial, there are six-sequence by period means, two in each treatment sequence group (AB, BA, and AA). The five resulting degrees of freedom can be decomposed into 2 for sequence, 1 for treatment, 1 for period, and 1 for carryover. In the trial, the primary efficacy endpoint will be analyzed (in the subjects in the Full Analysis Set randomised to the AB/BA groups) by using a

mixed effect linear model with period, sequence, stratification factor (use of prophylactic therapy with C1 INH, which was derived by long-term prevention with C1 INH at randomization), and treatment as fixed effects, and subject nested within sequence as a random effect. The mean treatment difference ($\mu_{C1 \text{ INH}} - \mu_{placebo}$) will be estimated with a 95% CI provided. The main analytic approach for the analysis of the PRO data will be similar and include only subjects randomised to the AB/BA groups, unless specified in the analyses section.

(Note: The Full Analysis Set is all subjects who have taken at least 1 dose of investigational product (the Safety Set) who have at least 1 post baseline (e.g., randomization) primary efficacy assessment.)

The trial was powered to demonstrate superior efficacy even in the presence of carryover effects. To assess any carryover effect, a sensitivity analysis excluded from the evaluation of the NNA any attacks occurring within the first 2 weeks of Study period 2 for both sequences when carryover is suspected to be maximal. Since carryover should occur only with the A/B treatment sequence, its effect (if present) will be to spread C1 esterase inhibitor [human] liquid for injection efficacy into the placebo study period, thereby diluting the efficacy of C1 INH and favouring the null hypothesis of the primary efficacy analysis; it is not anticipated that any placebo effect will similarly benefit C1 esterase inhibitor [human] liquid for injection within the B/A treatment sequence.

3. ANALYSIS OBJECTIVES

3.1 Analysis of PRO data

The main objectives of the analyses of the PRO data collected in SHP616-300 are:

- 1. To describe AE-QoL, WPAI-GH, SDS, and AAS scores by treatment and period (absolute, change and percentage change from baseline at each scheduled visit for AB, BA, and AA sequences) and assess differences between treatments (A or B), controlling for study period (1 or 2) and sequence (AB, BA) (change and percentage change).
- 2. To describe and estimate whether the effect of an attack on EQ-5D-5L index and EQ-VAS scores differs between treatments (A or B), controlling for study period (1 or 2) and sequence (AB, BA).
- 3. To describe and assess differences in the proportion of subjects achieving the responder definition (RD) in AE-QoL and AAS scores from baseline to final assessment between treatments (A or B), controlling for study period (1 or 2) and sequence (AB, BA).

The exploratory objective is:

1. To explore the relationship between efficacy (as defined in the protocol) and scores on the AE-QoL, WPAI-GH, SDS, and AAS (Hypothesis: Subjects with improved efficacy also have improved scores).

3.2 Analysis of HRUA-HAE data

The main objective of the analysis of the HRUA-HAE data collected in SHP616-300 is:

1. To describe HRUA-HAE (absolute values) according to treatment, study period (1 or 2) and sequence (AB, BA).

4. STUDY MEASURES

4.1 **Responder Definition (RD)**

A RD is the absolute change value, at an individual patient level, which indicates that a meaningful change in a PRO instrument score has occurred.

When no RD has been estimated, it has been proposed that a one-standard error measurement (one-SEM) criterion, or equivalently 0.5 standard deviations (SDs) when the reliability of the instrument is \geq 0.75, can be used as a proxy for minimal change (Norman et al., 2003). This distribution-based method provides the smallest change which, for an individual, is likely to be beyond the measurement error of the instrument, thus understood to represent true change. However, it is not known whether this change is clinically relevant. While not acceptable as a RD in itself, this distribution-based approach provides boundary information as any value proposed as a RD will need to be at least as large to rule out the possibility of responder classification occurring by chance.

In the absence of any known RDs in the HAE, or any other population, RDs for minimal change will be estimated using one-half a SD in the study baseline (Visit 1a) AE-QoL, EQ-5D-5L and AAS scores. It is reasonable to assume that these instruments have reliabilities of \geq 0.75. This estimate is based on the distributional characteristics of the sample under study. In addition, a number of pre-defined values (based on existing estimates for the minimal clinically important difference (MCID) or RD) will be applied in a sensitivity type analysis.

4.2 **PRO Measures and Scoring**

4.2.1 Angioedema Quality of Life (AE-QoL) Questionnaire

The AE-QoL questionnaire is a self-administered validated angioedema disease-specific quality of life instrument (Weller et al., 2012). Each of the 17 items has a five-point response scale ranging from 1 (Never) to 5 (Very Often). The questionnaire will be scored according to the developers' guidelines (Weller et al., 2012) to produce a total score and four domain scores (functioning, fatigue/mood, fear/shame, nutrition). Raw domain scores (mean of the item scores within each scale) and the raw total score (mean of all item scores) will be rescaled using linear transformations into final percentage scores ranging 0 to 100, based on the maximum possible score, where the higher the score the greater the QoL impairment. The minimal clinically important difference (MCID) for the total score is 6 (Weller et al., 2016). However, there is no evidence on the MCID/RD for the AE-QoL *domain* scores. Therefore, in addition to applying the

value of 6 for the total score, the method of using 0.5 SD in baseline domain scores will be used to determine the RD:

- Rescaled AE-QoL total score = 6, Baseline SD*0.5
- Rescaled AE-QoL functioning domain score = 6, Baseline SD*0.5
- Rescaled AE-QoL fatigue/mood domain score = 6, Baseline SD*0.5
- Rescaled AE-QoL fear/shame domain score = 6, Baseline SD*0.5
- Rescaled AE-QoL nutrition domain score = 6, Baseline SD*0.5

4.2.2 EuroQol 5-dimensional 5-level (EQ-5D-5L) descriptive system and EQ Visual Analogue Scale (EQ-VAS)

The EQ-5D-5L is a standardized measure of health status comprised of a descriptive system including five health-related quality of life states (i.e., mobility, self-care, usual activities, pain/discomfort, and anxiety/depression) and a VAS of overall health. Each dimension is rated on a 5-point response scale indicating severity of problems, where 1 is "no problems" and 5 is "extreme problems". The five questions are scored and together contribute to the EQ-5D-5L index (utility) score between 0 and 1 (1 being perfect health), which will be calculated using the developers' algorithm based on country-specific reference score sets (Van Hout et al., 2012). Score sets are available for Denmark, France, Germany, Japan, Netherlands, Spain, UK, US and Zimbabwe. For countries in which no score set exists (Canada, Hungary, Israel, Romania, and Sweden) the closest neighboring country will be used as a proxy (EuroQol Group, 2015).

The EQ-VAS is a measure of overall self-rated health status, used and analyzed separately from the index score. The EQ-VAS records the subject's self-rated health on a 20-cm vertical VAS with endpoints labelled "the best health you can imagine" and "the worst health you can imagine". The EQ-VAS score ranges from 0 to 100, with higher scores indicative of better overall health.

4.2.3 Work Productivity and Activity Impairment – General Health (WPAI-GH)

The WPAI-GH is a 6-item questionnaire assessing work and activity impairment due to health problems during the past 7 days. It will be scored for each assessment according to the scoring guidelines listed below (Reilly et al., 1993). The instrument elicits four main scores in relation to general health specifically: absenteeism (the percentage of work time missed because of one's health in the past seven days), presenteeism (the percentage of impairment experienced while at work in the past seven days because of one's health), overall work productivity loss (an overall impairment estimate that is a combination of absenteeism and presenteeism), and activity impairment (the percentage of impairment in daily activities because of one's health in the past seven days). The domains are calculated as follows:

- 1. Absenteeism (work time missed = (Q2/(Q2+Q4))*100)
- 2. Presenteeism (impairment at work or reduced on-the-job effectiveness = (Q5/10)*100)
- 3. Work productivity loss (overall work impairment/absenteeism plus presenteeism = (Q2/(Q2+Q4)+[(1-(Q2/(Q2+Q4)))x(Q5/10)])*100)
- 4. Activity Impairment = ((Q6/10)*100)
The scores are percentages with higher values indicating greater percentage impairment.

4.2.4 Sheehan Disability Scale (SDS)

The SDS is a 5-item, self-rated questionnaire designed to measure the extent to which a person's disability due to an illness or health problem interferes with each of the following three dimensions: work/school, social life/leisure activities, and family life/home responsibilities (Sheehan, 1983). Three items ask subjects to rate the extent to which three aspects of daily life are impaired by his or her symptoms using a 10-point scale. Two items ask subjects how many days have been lost or unproductive in the last week. A total global functioning impairment score is calculated as the sum of the three individual dimensions, ranging from 0 (unimpaired) to 30 (highly impaired), with higher scores indicative of greater impairment. The raw numerical scores will also be rescaled to a percentage of the maximum score (Sheehan, 1983). Higher scores show greater impairment.

4.2.5 Angioedema Activity Score (AAS)

The AAS collects information of disease activity in the last 24 hours. The following items are assessed: experience of swelling, severity of the swelling, timing of the swelling, extent of discomfort due to the swelling, extent that the swelling caused limitations in daily life, and feelings of being disfigured by the swelling. The instrument uses a binary response option for the first item and a three-point response scale for the 5 items thereafter. Total scores range between 0 and 15 points (Weller et al., 2013). The total disease activity score for the duration of an entire study period is the sum of each daily score post-treatment in each 14-week study period – the 98-day AAS. The weekly average daily disease activity scores will also be calculated for each study week, and compared with the baseline day score, for each study period. An overall daily average AAS score will also be calculated for each study period.

The MID for a 7-day total score is 8 (Weller et al., 2013). This is equivalent to a MID of 64 for a 14-week study period and around 1 for an average daily score. In the absence of known MCIDs or RDs for the AAS in HAE, the MID will be used as well as one-half of the SD of baseline scores as an MCID/RD estimate:

- AAS Index Score = 1, Baseline SD*0.5
- AAS VAS Score = 1, Baseline SD*0.5

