4.2 Exclusion Criteria

Subjects are excluded from the study if any of the following exclusion criteria are met.

1. Adults (≥ 18 years of age) receiving prophylactic IV CINRYZE that exceeds the approved dosing regimen of 1000 U every 3 or 4 days (receiving a weekly dose > 2000 U).
2. Adolescents (≥ 12 and < 18 years of age) currently receiving prophylactic therapy with C1 INH (not applicable to Germany and Israel).
3. Have had signs or symptoms of an angioedema attack within 2 days prior to the first dose of the investigational product in Treatment Period 1.
4. Have received any C1 INH therapy or any blood product for the treatment or prevention of angioedema attacks within 3 calendar days prior to the first dose of investigational product in Treatment Period 1.
5. If female, have started or changed the dose of any hormonal contraceptive regimen or hormone replacement therapy (ie, estrogen/progestin containing products) within 2 months prior to the screening visit.
6. Have a history of hypercoagulability (abnormal blood clotting) or other predisposition for thromboembolism.
7. Have a diagnosis of acquired angioedema or known presence of anti-C1 INH antibodies.
8. Have a history of allergic reaction to C1 INH products, including CINRYZE (or any components of CINRYZE), other blood products, or Firazyr (icatibant).
9. Be pregnant or breastfeeding.

10. Have received an investigational drug within 30 days prior to the first dose of investigational product in Treatment Period 1.
11. Have, as determined by the investigator and/or the sponsor's medical monitor, any surgical or medical condition (including positive for hepatitis B, hepatitis C, or HIV infection; alcohol, drug, or medication abuse within 1 year before screening; or mental condition rendering the subject or parent(s)/legal guardian unable to understand the nature, scope of the study, and possible consequences of the study), or relationship to study staff or sponsor (including people accommodated in an institution as well as people who are dependent on the sponsor, CRO, site or the investigator) that could interfere with the administration of investigational product or interpretation of study results.

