7.1.2.2 Visit 1a (postdose)

The following procedures will be performed after the administration of the first dose of investigational product at Visit 1a:

- Collection of AEs
- Recording in the electronic subject diary any symptoms or occurrences of an angioedema attack (and the subject diary is to be updated daily; Section 7.2.2.2).
- Vital signs (≤ 10 min after the end of the injection and between 30 min and 1 hour after the end of the injection)
- Injection site reaction assessment (15 min, 30 min, and 1 hour after the end of the injection)
- Recording the daily AAS in the electronic subject diary

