Objective 2: To describe and estimate whether the effect of an attack on EQ-5D-5L index and EQ-VAS scores differs between treatments (A or B), controlling for study period (1 or 2) and sequence (AB, BA).

The change in EQ-5D index and EQ-VAS scores from the previous assessment to the first attack during a study period will be summarised using appropriate descriptive statistics (e.g. mean and SD, range, median, and interquartile range). The EQ-5D-5L index and EQ-VAS scores at subsequent attacks will also be described. All data will be presented for each subject group (AB, BA, AA), for each treatment (A or B) within each study period (1 or 2). The data will be presented in Table 2.1.1 and Table 2.1.2.

These tables for the AB and BA subject groups will allow informal assessment of whether there is a) a treatment effect, b) a sequence effect, c) a period effect, and d) and treatment by period interaction. A treatment by period interaction occurs when the effect of the treatment/placebo depends on the period in which it was administered. For example, if there is a carry-over effect of active treatment (the effect of the treatment persisting beyond the period in which it was

administered), then the placebo effect would be expected to be larger in period 2, when it follows the active treatment, than in period 1 when it precedes it.

Objective 3: To describe and assess differences in the proportion of subjects achieving the responder definition (RD) in AE-QoL and AAS scores from baseline to final assessment between treatments (A or B), controlling for study period (1 or 2) and sequence (AB, BA).

Frequencies and percentages will be used to summarize the proportion of subjects achieving the RD on the AE-QoL and AAS from baseline to end of each study period. For the AAS this will be the change from baseline to the average daily score during the last 7 days of the study period. The data will be presented for each subject group (AB, BA, AA), presenting the frequencies for each treatment (A or B) within each study period (1 or 2). Results will be tabled in a form similar to that shown below:

	Sequer	ice A/B	Sequen	ice B/A	Sequer	ce A/A	То	tal
PRO Measure	Period 1: 2000 IU Cinryze (N=xx)	Period 2: Placebo (N=xx)	Period 1: Placebo (N=xx)	Period 2: 2000 IU Cinryze (N=xx)	Period 1: 2000 IU Cinryze (N=xx)	Period 2: Placebo (N=xx)	Placebo (N=xx)	Placebo (N=xx)
AE-QoL								
n	xx	xx	XX	xx	XX	XX	XX	xx
Percent	xx.x%	xx.x%	xx.x%	xx.x%	xx.x%	xx.x%	xx.x%	xx.x%
AAS								

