Achieving the Responder Definition of 6 in Angioedema Quality of Life
Questionnaire Nutrition Score from Baseline (Visit 1a) to Week 13 of Each Study
Period by Treatment
- Table 3.2.1:Frequencies and Percentages of Subjects Reaching the Responder Definition of
One-half a Standard Deviation of the Common Baseline of 1.33 for Change in
Weekly Average Angioedema Activity Daily Score from Baseline (Day 1) to
Week 14 by Treatment Sequence and Period
- Table 3.2.2:Frequencies and Percentages of Subjects Reaching the Responder Definition of 1
for Change in Weekly Average Angioedema Activity Daily Score from Baseline
(Day 1) to Week 14 by Treatment Sequence and Period
- Table 3.2.3:Mixed Effects Logistic Regression Model Results for Proportion of Subjects
Achieving the Responder Definition of One-half a Standard Deviation of the
Common Baseline (1.33) in Weekly Average Angioedema Daily Score from
Baseline (Day 1) to Week 14 of Each Study Period by Treatment
- Table 3.2.4:Mixed Effects Logistic Regression Model Results for Proportion of Subjects
Achieving the Responder Definition of 1 in Weekly Average Angioedema
Activity Daily Score daily from Baseline (Day 1) to Week 14 of Each Study
Period by Treatment

8.4 Exploratory Objective 1

- Table 5.1.1:Mixed Effects Regression Model Results of the Relationship between Normalized
Number of Attacks and Change in Angioedema Quality of Life Questionnaire
Total Score from Baseline (Visit 1a) to Week 13 of Each Study Period
- Table 5.1.2:Mixed Effects Regression Model Results of the Relationship between Normalized
Number of Attacks and Change in Angioedema Quality of Life Questionnaire
Functioning Score from Baseline (Visit 1a) to Week 13 of Each Study Period
- Table 5.1.3:Mixed Effects Regression Model Results of the Relationship between Normalized
Number of Attacks and Change in Angioedema Quality of Life Questionnaire
Fatigue/Mood Score from Baseline (Visit 1a) to Week 13 of Each Study Period
- Table 5.1.4:Mixed Effects Regression Model Results of the Relationship between Normalized
Number of Attacks and Change in Angioedema Quality of Life Questionnaire
Fear/Shame Score from Baseline (Visit 1a) to Week 13 of Each Study Period
- Table 5.1.5:Mixed Effects Regression Model Results of the Relationship between Normalized
Number of Attacks and Change in Angioedema Quality of Life Questionnaire
Nutrition Score from Baseline (Visit 1a) to Week 13 of Each Study Period

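### The HRQoL SAP judges AAS response and percentage change from one Day 1 score that entry criteria push toward zero, and gives two conflicting baselines for Period 2

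*SAP*

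**What the plan says.** **The score.** HRQoL SAP 4.2.5: "The AAS collects information of disease activity in the last 24 hours", and "Total scores range between 0 and 15 points". Weekly averages are "compared with the baseline day score, for each study period". For Objective 3, section 6.4.1 adds: "For the AAS this will be the change from baseline to the average daily score during the last 7 days of the study period".

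**The thresholds.** Sections 4.2.5 and 10.3 set the responder definition at 1 point and at half the baseline SD. The title of Table 3.2.1 already carries the second value: "One-half a Standard Deviation of the Common Baseline of 1.33 for Change in". The title of Figure 3.2 makes clear that response means improvement. Section 6.4.1 also tabulates percentage change from baseline.

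**Entry and timing.** Protocol 4.2, exclusion 3, removes subjects who "Have had signs or symptoms of an angioedema attack within 2 days prior to the first dose" of Period 1. The item "Recording the daily AAS in the electronic subject diary" is in the Visit 1a postdose list (Protocol 7.1.2.2) and not in the predose list (7.1.2.1). No run-in AAS is planned.

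**Period 2 baseline.** HRQoL SAP 5.1.2 gives mixed models a common Visit 1a baseline. Titles of the AAS model tables say Day 1, which the protocol's schedule equates with Visit 1a. Section 10.2 subtracts the Visit 1b score in Period 2 without exception, and the models in 6.4.1 adjust for baseline at either visit.

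**The concern.** A responder definition is useful only if subjects have room to respond. Here the recall window of the baseline score is shorter than the attack-free window needed for entry, so the Period 1 baseline is likely to sit at or near the floor of the scale. A subject at the floor is a non-responder on active and on placebo whatever the drug does, and so contributes nothing to the comparison of responder proportions. Few AAS responders could then be read as lack of benefit when the cause is arithmetic.

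Using Visit 1b for Period 2 removes the entry restriction but brings a different problem. There is no washout (Protocol 3.1), so that single day reflects the Period 1 treatment. If the drug works, A/B subjects are judged on placebo from a lowered baseline and B/A subjects are judged on active from a raised one. Response then depends on sequence by construction.

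**Working it through.** **1. The plan's own figures.** The cited minimal difference is 8 for a 7-day total: 8/7 = 1.14 a day, which agrees with the stated value of around 1. The 14-week equivalent is given as 64, but 8 × 14 = 112 (64 is 8 weeks). It is not used as a threshold but could be corrected in the same edit. The printed half-SD of 1.33 means a baseline SD of 2 × 1.33 = 2.66.

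**2. The floor.** The largest possible improvement is baseline minus 0. From 0 it is 0, below both thresholds. Daily scores are whole numbers, so the 1-point rule needs a baseline of at least 1 and the 1.33 rule needs at least 2. Percentage change divides by the baseline and is undefined at 0.

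**3. Can the SD show how many are at zero?** If a share p is non-zero, with mean m and SD s, then p(s² + m²) − p²m² = 2.66². This quadratic generally has two roots:
- m = 5, s = 2: p = 0.349 or 0.811
- m = 8, s = 0: p = 0.127 or 0.873
- s = 2.66: p = 1 is a solution for any m

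The SD shows that baselines were not all zero. It does not show that most were.

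**4. Share with symptoms on Day 1 after two attack-free days.** Attack durations and enrolled attack rates are not in the documents; entry requires at least 2.0 a month. I assume r = 2 to 8 attacks per 30.4 days, each lasting d = 1 to 3 days. Continuous form: 1 − exp[−r/(30.4 − rd)]. Discrete form, allowing for the compulsory symptom-free day between attacks: r/(30.4 − rd − r), capped at 1.

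| r | d = 1 | d = 2 | d = 3 |
|---|---|---|---|
| 2 | 6.8% / 7.6% | 7.3% / 8.2% | 7.9% / 8.9% |
| 4 | 14.1% / 17.9% | 16.4% / 21.7% | 19.5% / 27.8% |
| 6 | 21.8% / 32.6% | 27.8% / 48.4% | 38.4% / 93.8% |
| 8 | 30.0% / 55.6% | 42.6% / 100% | 71.3% / undefined |

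(continuous / discrete)

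At 2 to 4 attacks a month, 7–28% have symptoms, so 72–93% start at zero. At 6 to 8 a month the answer depends on duration and formula, and fewer than half may be at zero.

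**5. Effect on Objective 3.** The crossover sequences hold 26 + 26 = 52 subjects. With a Visit 1a baseline and 7–28% non-zero, 52 × 0.07 = 3.6 and 52 × 0.28 = 14.6, so about 4 to 15 subjects per period could respond at all. The logistic model in 6.4.1 has fixed effects for treatment, baseline, age, gender, country, prophylaxis, period, sequence and carry-over.

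**6. Effect on the Objective 1 change model.** Let Y be the final-week score and B the baseline. A model of Y − B with B as a covariate has the same treatment coefficient as a model of Y with B as a covariate; only the coefficient of B changes, by 1. If B is Visit 1a in both periods, (Y_active − B) − (Y_placebo − B) = Y_active − Y_placebo. The contrast does not depend on where B sits.

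**The case against.** A reader might infer that most subjects certainly start at zero and that the AAS analyses therefore cannot measure benefit. The documents do not support that. They give no share at zero, the SD is compatible with high or low shares (step 3), and the attack-rate calculation rests on assumptions that can reverse it (step 4). By step 6 the modelled Objective 1 contrast survives a common Visit 1a baseline; raw change may look flat or adverse, but it would do so under both treatments.

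Other points for the plan:
- Postdose recording matters little. A 24-hour recall also covers predose hours, and median time to peak was 36–48 hours in the Phase 1 study (Protocol 1.2.2.2).
- The protocol's AAS endpoint, the 98-day score, needs no baseline and is analysed with the mixed model of main SAP 10.4. HRQoL SAP 10.1.5 and Table 1.4.1 add period totals and averages.
- Percentage change is only tabulated. All of this lies outside the tested hierarchy.
- Section 5.1.2 could be read as resolving Period 2: Visit 1a for models, Visit 1b for descriptive tables.

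The first three stand and limit the scope. The last does not fully stand, because 6.4.1 allows either visit within the models and 10.2 makes no exception for them. Nor does adjusting the logistic model for baseline help: it cannot make response possible for a subject at zero.

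**Conclusion.** The point holds for the AAS responder analysis and the AAS percentage-change summaries of the HRQoL SAP. Three things follow from the text alone: the baseline is one 24-hour score taken just after a required attack-free window; a subject at zero cannot respond on either treatment; and the Period 2 baseline is stated inconsistently.

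The size is conditional. About 72–93% are at zero if attacks run at 2 to 4 a month and last 1 to 3 days, and possibly under half at higher rates. The entry restriction does not apply at Visit 1b, so the floor reaches Period 2 only if Visit 1a is the common baseline. Otherwise the problem is a baseline shaped by the Period 1 treatment.

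The primary endpoint, the main SAP's 98-day AAS and the baseline-adjusted Objective 1 contrast under a common Visit 1a baseline are unaffected. This should be corrected, but it concerns a supplementary analysis.

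**What to change.** - State one Period 2 baseline rule and align HRQoL SAP 5.1.2, 6.4.1, 10.2 and the table titles with it.
- Drop AAS responder status and AAS percentage change from Day 1 (Tables 1.4.4 and 3.2.1 to 3.2.4, Figure 3.2). Alternatively, label them descriptive and report the number of subjects with a zero baseline by sequence and period. The printed 1.33 implies that baseline scores have already been summarised, so this count should be easy to produce.
- Base the AAS treatment comparison on the weekly-average and 98-day scores, using the mixed model in main SAP 10.4.

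A responder defined on each subject's placebo-minus-active difference could be added, but it gives one status per subject and so would not answer Objective 3, which compares proportions between treatments.

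The cost is HRQoL SAP wording and a few table shells; the daily scores are already planned for collection. What is lost is an AAS responder table in a supplementary analysis.
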